5.3. Adjustments for Covariates

Analyses of all efficacy variables and patient-reported outcome variables defined in Sections 5.2.1.1 and 5.2.1.3 will be stratified using the randomization stratification factors listed below (defined based on IWRS data). Sensitivity analyses may also be performed to include additional stratification factors, non-stratified, or covariate adjusted analyses (for example, Cox models with covariates).

- Number of prior systemic therapies for advanced/metastatic disease (0 versus ≥ 1)
NOTE: Any therapy administered in the adjuvant/neoadjuvant setting will not be considered as a prior line of therapy here.
- Histological tumor type (LMS versus liposarcoma versus pleomorphic sarcoma versus other STS types)
- ECOG performance status (0 versus 1)

Prospectively planned sensitivity, subgroup, and multivariate analyses are described in more detailed in Section 5.11.4.

Other baseline covariates that may be of interest include (but may not be limited to) the following:

- liver lesions (presence at baseline vs. absence at baseline)

- lung lesions (presence at baseline vs. absence at baseline)
- sex (females vs. males)
- age
- weight
- duration of disease since diagnosis
- grade of STS at diagnosis (1/low vs. 2/intermediate vs. 3/high)
- albumin level
- prior systemic therapy in the adjuvant or neo-adjuvant setting (none vs. any)
- prior systemic anti-cancer therapy (none vs. any)
- alanine aminotransferase (ALT)
- bone lesions (presence at baseline vs. absence at baseline)
- prior radiation therapy (none vs. any)
- duration of most recent prior systemic therapy
- hemoglobin
- platelets
- leukocytes

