5.13. Patient-Reported Outcome Analyses

For each instrument, percentage compliance will be calculated as the number of completed assessments divided by the number of expected assessments (that is, patients still on study). Percentage compliance will be summarized by treatment group and overall. Similarly, the reasons for non-compliance will also be summarized descriptively.

Time-to-event variables will be analyzed using stratified log-rank tests (analogous to the primary analysis) for comparisons between study arms, stratified Cox models (for between-arm statistics including the treatment HR), and Kaplan-Meier method (for within-arm statistics).

Data will also be summarized descriptively for all of the variables identified Section 5.2.1.3, including shift tables.

QLQ-C30

Percentages of patients categorized as “improved” will be summarized and compared between study arms. Maximum improvement and worsening scores will be analyzed as continuous variables and compared between study arms using analysis of covariance (with both parametric and non-parametric p-values reported).

For the Physical functioning (PF2) as well as Emotional functioning (EF) scales, the change from baseline will be further analyzed by using mixed-effect repeated measures models based on restricted maximum likelihood estimation. Fixed effects in the model will include study treatment arm, baseline score, cycle number, and interaction term for study treatment arm and cycle number. The variance-covariance matrix that results in the minimum Akaike Information Criterion (Akaike 1973) from among unstructured, variance components, auto-regressive, and compound symmetric will be incorporated in the model. To implement the variance structure, patients will be included in the model as a random effect. The magnitude of the main effects and interactions will be evaluated and discussed. Based on the model-based means (LSMeans) from the repeated measures model, treatment group contrasts will be tested for each cycle number separately. Treatment group contrasts also will be tested for the treatment group marginal means.

Floor and ceiling effects will be summarized for each of the 15 scales. The presence of a significant ceiling effect suggests that not much improvement is possible for that scale. Likewise the presence of a floor effect suggests that worsening is less likely.

Modified Brief Pain Inventory – short form (mBPI-sf)

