Percentages of patients categorized as “improved” will be summarized and compared between study arms. Similarly, percentage of patients achieving a clinical pain response will be summarized and compared between study arms. The cumulative distribution of the percentage of pain responders by treatment arm as a function of time is to be presented graphically. Maximum improvement and worsening scores will be analyzed as continuous variables and compared between study arms using analysis of covariance (with both parametric and non-parametric p-values reported).

Individual pain items on the mBPI-sf (that is, worst, least, average, and current pain) will be described using descriptive statistics by treatment arm and cycle. A mixed effects repeated measures model will be applied to compare between treatment arms, which may be adjusted for other covariates. Similar analyses will also be conducted for the mean of 7 pain interference with function items.

EQ-5D-5L

The EQ-5D-5L responses for each item will be summarized by frequency and corresponding percentages by treatment arm and cycle. Descriptive statistics (mean, standard deviation, median, minimum and maximum) for the index and VAS will be calculated and presented by treatment arm and cycle. Additionally, the change from baseline will also be presented. The index score

between treatment arms will be compared using mixed models. The model will include baseline score as a covariate and an unstructured covariance matrix will be utilized. A similar analysis will be performed on the VAS scores.

Of interest is a significant time-by-group interaction for each of the items, addressing whether treatment group profiles are different over time (from randomization through the last assessment following discontinuation).

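### SAP 5.3 calls for stratified analyses of the PRO variables, but the PRO mixed models and percentage comparisons in SAP 5.13 do not carry the stratification factors through

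*SAP*

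**What the plan says.** SAP 5.3 sets the general rule: "Analyses of all efficacy variables and patient-reported outcome variables defined in Sections 5.2.1.1 and 5.2.1.3 will be stratified using the randomization stratification factors", using IWRS values. The factors are the number of prior systemic therapies (0 versus at least 1), histology in four groups, and ECOG PS (0 versus 1). Region is not listed. Departures appear only as an option: "Sensitivity analyses may also be performed to include additional stratification factors, non-stratified, or covariate adjusted analyses". The variables defined in 5.2.1.3 include change from baseline, improved status and clinical pain response, so the rule reaches all of them.

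SAP 5.13 then describes the analyses:

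- **Time-to-event PROs:** "Time-to-event variables will be analyzed using stratified log-rank tests (analogous to the primary analysis) for comparisons between study arms". This agrees with 5.3.
- **QLQ-C30 physical and emotional functioning, mixed model:** "Fixed effects in the model will include study treatment arm, baseline score, cycle number, and interaction term for study treatment arm and cycle number". No stratification factor is named.
- **mBPI-sf:** "A mixed effects repeated measures model will be applied to compare between treatment arms, which may be adjusted for other covariates". There is no list of fixed effects.
- **EQ-5D-5L index, with a similar analysis for the VAS:** "The model will include baseline score as a covariate and an unstructured covariance matrix will be utilized". No other covariate is named.
- **Percentages improved or with a clinical pain response:** to be compared between arms, with neither a test nor strata given.

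For ORR and DCR, by contrast, SAP 5.11.3.2 and 5.11.3.3 name a Cochran-Mantel-Haenszel test adjusted for the stratification variables.

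**The concern.** Randomization was stratified by these factors plus region (protocol 9.3, 48 cells), so the arms are close to balanced on them by design. A model that leaves out a prognostic, balanced factor keeps the between-stratum variation in its residual. The treatment estimate is then about as stable as the design makes it, but the reported standard error does not show this: intervals are too wide and tests reject too rarely.

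Prognostic value is plausible for ECOG PS, which separates fully active patients from those restricted in strenuous activity (protocol Attachment 4). That is close to what the physical functioning scale measures.

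There is also a specification problem whatever the prognostic strength. Section 5.13 neither refers back to 5.3 nor labels these models as sensitivity analyses, so two programmers could build different models from the same SAP. PROs are a secondary objective, and their model should be settled before unblinding.

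**Working it through.** The documents give no standard deviation, effect size or power for any PRO mixed model, so there is no stated figure to reproduce. The check asks how much the factors could matter.

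**Inputs from the documents.** 460 patients, 1:1 (SAP 5.1). Two-sided alpha 0.05 (SAP 5.2). Degrees of freedom for the factors: 1 + 3 + 1 = 5 as main effects, or 2 × 4 × 2 − 1 = 15 as 16 cells. As the low end for patients per cycle, 25% of 460 = 115, from the EQ-5D-5L rule in SAP 5.2.1.3.

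**Assumptions.** Partial R² of the factors given baseline score: 0 to 0.15. Blocks of 4 within the 48 cells. Factor prevalences, such as 40% ECOG PS 1 and 30% with prior therapy. An ANCOVA on one score per patient stands in for the marginal contrast of the repeated-measures model, with no dropout.

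**Step 1: formula that ignores balancing.** SE ratio, with versus without the factors = √[(1 − R²)(n − 3)/(n − 3 − p)]. At n = 460, p = 5 and R² = 0.10: √(0.90 × 457/452) = 0.954. Adjustment breaks even at R² = p/(n − 3):

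| n | 5 df | 16 cells (15 df) |
|---|---|---|
| 460 | 5/457 = 1.1% | 15/457 = 3.3% |
| 115 | 5/112 = 4.5% | 15/112 = 13.4% |

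**Step 2: simulation with stratified randomization** (3,000 trials per setting, main effects). Change in the mean model SE when the factors are added:

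| Assumed R² | n = 460 | n = 115 |
|---|---|---|
| 0 | +0.1% | +0.9% |
| 0.02 | −1.0% | −0.1% |
| 0.05 | −2.4% | −1.7% |
| 0.10 | −5.1% | −4.3% |
| 0.15 | −7.8% | −7.0% |

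**Step 3: where the loss sits.** At n = 460 and R² = 0.10 the model without the factors reports a mean SE of 0.0934 against a true spread of 0.0879 (0.0934/0.0879 = 1.06), with type I error about 0.038. With the factors, the SE is 0.0887 against 0.0873. The true spread barely changes; the reported SE does. Simulation noise is about 0.4 points on a 5% size and about 1.3% on each spread. As a cross-check, under perfect balance the unadjusted SE is too wide by 1/√0.90 = 1.054 and the size is 2Φ(−1.96/√0.90) = 0.039, in line with the simulation.

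**Step 4: power.** Take an effect of 1.960 + 0.842 = 2.802 unadjusted model SEs, nominally 80% power. Under perfect balance, power without the factors is Φ(0.842/√(1 − R²)), and with them Φ(2.802/√(1 − R²) − 1.960):

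| Assumed R² | Without | With | Gain (points) |
|---|---|---|---|
| 0.02 | 80.2% | 80.8% | 0.5 |
| 0.05 | 80.6% | 82.0% | 1.4 |
| 0.10 | 81.3% | 84.0% | 2.7 |
| 0.15 | 81.9% | 86.0% | 4.0 |

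Comparing the adjusted power with a flat 80% would overstate the gain, because the balanced design already lifts the unadjusted power slightly.

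**The case against.** The strongest reply is that nothing conflicts. Section 5.3 is the general rule and covers these variables. Section 5.13 says what the fixed effects will include, not that they include nothing else. The EQ-5D-5L sentence is plainly a partial description: it names neither arm nor time, although the same section compares arms and is interested in a time-by-group interaction. An unnamed test for the percentages is under-specification, which 5.3 already governs. This stands in part. A reader might infer that 5.13 overrides 5.3 and that the factors will be left out; the documents do not go that far. But they do not settle the matter either: the time-to-event text in the same section restates the stratification, and the optional mBPI-sf adjustment sits poorly beside the firm wording of 5.3.

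A reader might also infer that the PRO standard errors are in fact too wide and that precision is given away for nothing. The documents do not support that. Baseline score is already in the QLQ-C30 and EQ-5D-5L models and may leave the factors little to explain. At R² = 0 nothing is lost, and at n = 115 even main effects need some prognostic value to pay for themselves.

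Nor do the documents support a claim that the missing-at-random assumption is weakened. They give no dropout by stratum, and the models already use baseline and observed follow-up scores.

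Finally, little hangs on the result. SAP 5.6 limits family-wise error control to OS, PFS and ORR, the QLQ-C30 model covers two of 15 scales, and protocol 10.2.3 keeps EQ-5D-5L responses out of the clinical study report. This supports a low priority, not leaving the text open.

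**Conclusion.** The gap between 5.3 and 5.13 is real and should be closed. It is a minor specification point. Its statistical cost is conditional on two things: that 5.13 is programmed literally, and that the factors predict PRO scores beyond baseline score. Under both, the model standard errors are somewhat too wide and the tests conservative. For an assumed partial R² of 0 to 0.15 at n = 460, adding the factors saves about 0 to 8% of the standard error, and about 1% at 0.02. These sizes rest on the assumed R², block size and prevalences, and on a single-score model without dropout. The direction of the error does not inflate type I error, and OS, PFS and ORR are untouched.

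**What to change.** In SAP 5.13, name prior systemic therapy (0 versus at least 1), histology (four levels) and ECOG PS (0 versus 1), all as IWRS values, as main effects in the QLQ-C30, mBPI-sf and EQ-5D-5L mixed models. Use main effects (5 df), not the 16 cells. The change applies to the ITT population, where SAP 5.7.1 places the PRO analyses. Compare the percentages improved and with a clinical pain response by Cochran-Mantel-Haenszel over the same strata, as is already done for ORR and DCR.

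The cost is SAP wording and one more line in each model; no new data are needed. The downside is a few degrees of freedom. In late cycles with few patients they may cost slightly more than they return if the factors are weakly prognostic: about 0.9% on the standard error at n = 115 and R² = 0 in the simulation.

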12.2.10. Analyses of Patient-Reported Outcomes (PROs)

Patient-reported outcomes are measured through the following:

- mBPI-sf (Brief Pain Inventory [Short Form] Modified)
- EORTC QLQ-C30 (The European Organization for Research and Treatment of Cancer Quality of Life Questionnaire Core 30)
- EQ-5D-5L (EuroQol 5-Dimension 5-Level)

For each instrument (mBPI-sf, EORTC QLQ-C30, and EQ-5D-5L), percentage compliance will be calculated as the number of completed assessments divided by the number of expected assessments (that is, patients still on study and alive). Percentage compliance and reasons for non-compliance will be summarized by treatment arm and time point.

Data will be separately summarized by treatment and time point using descriptive statistics. The main efficacy measure for the pain endpoint will be the time to first worsening of the mBPI-sf “worst pain” score. Time to first worsening in pain will be described using the method of Kaplan and Meier and analyses will be made between the 2 arms by a log-rank test. “Worsening” will be defined as either a “worst pain” increase of ≥ 2 points postbaseline (Farrar et al. 2001; Rowbotham 2001) or an analgesic drug class increase of ≥ 1 level. However, other approaches to defining clinically meaningful worsening in pain might be considered. Further details will be provided in the SAP.

Additionally, time to first worsening of QLQ-C30 scale scores (see Section 10.2) will be analyzed using Kaplan-Meier and Cox methods. Further statistical analysis to be performed for PROs will be defined and detailed in the SAP.

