5.2. General Considerations

This document describes the statistical analyses planned prior to final treatment assignment unblinding of the aggregate database. Any change to the data analysis methods described in the protocol will require an amendment ONLY if it changes a principal feature of the protocol. Any other change to the data analysis methods described in the protocol and the justification for making the change will be described in the clinical study report (CSR). Additional exploratory analyses of the data will be conducted as deemed appropriate.

All tests of treatment effects will be conducted at a two-sided alpha level of 0.05 unless otherwise stated, and all confidence intervals (CIs) will be given at a two-sided 95% level, unless otherwise stated. Statistical analysis will be performed using SAS software (SAS, Version 9.1.2 or higher).

The following general terms will be used globally in the SAP:

- Unless otherwise specified, summary statistics stand for n, mean, standard deviation, median, minimum, and maximum for continuous variables; and frequency and percentage for categorical variables.
- **Study Treatment Period:** begins on the day the first dose of study treatment is administered and ends when the patient and the investigator agree that the patient will no longer continue study treatment. The date of this agreement is to be reported on the electronic case report form (eCRF) as the Date of Discontinuation from study treatment.
- **Postdiscontinuation Follow-Up:** begins the day after the patient and the investigator agree that the patient will no longer continue study treatment.

Short-term follow-up begins the day after the patient and the investigator agree that the patient will no longer continue study treatment and lasts approximately 30 days (± 7 days) (until the short-term 30-day safety follow-up visit is completed).

Long-term follow-up begins the day after short-term follow-up is completed and continues until the patient's death or overall study completion (whichever is earlier).

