The mBPI-sf assesses the severity of pain and its impact on functioning. The assessment will be analyzed primarily in terms of the “worst pain” score from each assessment. The first assessment will occur at Cycle 1 Day 1. **Time to first worsening of the mBPI-sf (Brief Pain Inventory Short Form Modified) “worst pain” score (TWP)** is defined for each patient as the time from the date of the first study drug dose (baseline date) to the first date of either a “worst pain” score increase of ≥ 2 points from baseline with no change in analgesic use or “worst pain” score increase of ≥ 1 point from baseline and an analgesic drug class increase of ≥ 1 level (Farrar et al., 2001; Rowbotham, 2001). If the patient has not worsened by either of these criteria, TWP will be censored for analysis on the last date the mBPI-sf was administered. Patients with a baseline worst pain score of 8 or more or with a missing baseline score (i.e. no assessment prior to or on the day of the first study drug dose) will not be included in the time to first worsening analysis.

A clinical pain response will be defined as a “worst pain” score decrease of ≥ 2 points from baseline with no change in analgesic use or a “worst pain” score decrease of ≥ 1 point from baseline and an analgesic use decrease of ≥ 1 level. Patients with a baseline worst pain score of 0 (best possible score) or with a missing baseline score will not be included in the analysis of this endpoint. The cumulative distribution of the percentage of pain responders by treatment arm as a function of time is to be presented graphically.

In addition to the TWP variable defined above, the following variables will be derived for the “worst pain” score:

- For each patient, change from baseline will be calculated for every postbaseline assessment by subtracting the baseline assessment result from the current assessment result.
- Maximum improvement and maximum worsening scores (over baseline) will be determined from the set of all postbaseline change scores.
- Maximum improvement and maximum worsening scores (over an assessment at start of monotherapy) will be determined from a set of change scores from 2nd monotherapy cycle onwards.
- A patient first improving over baseline by 2 points or more without prior worsening of 2 points or more will be categorized as having “improved” his/her score during the study.

EQ-5D-5L

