5.7.1. Analysis Populations

Unless otherwise specified, all analyses will be based on the population of patients enrolled in the main protocol (Cohort 1). Patients enrolled under the extended enrollment addendum in Taiwan will be referred to as Cohort 2. Patients enrolled in Cohort 2 will not be included in the primary analysis of overall survival. As necessary, efficacy and safety analyses will be summarized for patients enrolled in Taiwan by pooling Cohort 1 and Cohort 2. All pooled analyses will be for descriptive purposes only.

[Table JGDJ.5.4](#) lists analysis population definitions and associated data type for analysis.

Table JGDJ.5.4. Analysis Populations

Population	Definition	Analysis Type / Variable	Note
Intention-to-treat (ITT) Population	All randomized patients	Baseline characteristics, concomitant medication, all efficacy analyses	Patients will be grouped according to randomized treatment.
Safety Population (SP)	All randomized patients who received any quantity of study drug	Safety, e.g. dosing/exposure, AE and resource utilization	Patients will be grouped according to treatment received as defined by the first dose received.
LMS subset of ITT Population	All randomized patients with LMS histologic subtype	Baseline characteristics, concomitant medication, all efficacy analyses	Patients will be grouped according to randomized treatment.

Abbreviations: AE = adverse event; ITT = intent-to-treat; LMS = leiomyosarcoma.

Compliance for the PRO instruments will be reported for the ITT population. All other PRO analyses will be on the ITT population and will include those from whom a completed PRO instrument was obtained at baseline and at least 1 postbaseline (either during study treatment period or 30-day postdiscontinuation follow-up period); thus, the actual patients included for each analysis will depend on the instrument and response variable.

A patient listing of analysis population details will be provided. This listing will be presented by treatment group and will include: investigator site, patient identifier, inclusion/exclusion flag for each population, and reason for exclusion from each population. All patients screened will appear on this listing.

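### The SAP does not require the baseline score in the mBPI-sf mixed model, although the trial collects it and the other PRO mixed models in the same section include it

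*SAP*

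**What the plan says.** SAP 5.13 plans a mixed model for three PRO instruments and specifies them unequally.

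- **mBPI-sf** (worst, least, average and current pain, and the mean of the seven interference items): "A mixed effects repeated measures model will be applied to compare between treatment arms, which may be adjusted for other covariates". No covariate is named. The response scale, time terms and covariance structure are not stated.
- **QLQ-C30** (physical and emotional functioning only): the response is change from baseline, and "Fixed effects in the model will include study treatment arm, baseline score, cycle number, and interaction term for study treatment arm and cycle number". The covariance structure is chosen by minimum AIC from four candidates.
- **EQ-5D-5L** (index, with a similar analysis for the VAS): "The model will include baseline score as a covariate and an unstructured covariance matrix will be utilized".

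SAP 5.2.1.3 says of the mBPI-sf: "The first assessment will occur at Cycle 1 Day 1". Under SAP 5.7.1, PRO analyses other than compliance "will include those from whom a completed PRO instrument was obtained at baseline and at least 1 postbaseline" form.

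SAP 5.3 stratifies PRO analyses by three randomization factors: prior systemic therapies, histology and ECOG status. It allows covariate-adjusted sensitivity analyses and gives an open list of other baseline covariates. No baseline PRO score is on that list.

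Protocol 12.2.10 names a different analysis as the main one for pain: "The main efficacy measure for the pain endpoint will be the time to first worsening of the mBPI-sf" worst-pain score.

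**The concern.** Baseline pain is the natural predictor of later pain on the same item. A model without it leaves explainable variation in the residual, and any chance difference between arms at baseline enters the treatment contrast. The SAP recognises this for two instruments and leaves it open for the third.

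The mixed model matters most for least, average and current pain and for the interference mean. The time-to-worsening, pain-response and maximum-change variables in SAP 5.2.1.3 are built on worst pain. For the other four outcomes the mixed model is the only between-arm comparison the SAP names.

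The wording is also permissive. SAP 5.2 sets the test level: "All tests of treatment effects will be conducted at a two-sided alpha level of 0.05 unless otherwise stated". SAP 5.6 confines type I error control to OS, PFS and ORR. For pain, prespecification is therefore the main protection, and here the covariates and the response scale can still be settled after results are known.

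**Working it through.** **What the documents give.** Power is stated only for OS. The ITT figure reproduces by the Schoenfeld formula with 322 events, HR 0.723 and one-sided alpha 0.02: √(322/4) × |ln 0.723| − 2.054 = 2.910 − 2.054 = 0.856, so power is 80.4% against the stated 80%. That has no bearing on pain. No power, effect size, standard deviation or baseline-to-follow-up correlation is given for any pain analysis, so there is no pain figure to reproduce.

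**Assumptions for the illustration.** Two-sided alpha of 0.05 (SAP 5.2); a reference effect detectable with 80% power without baseline; one follow-up visit; equal variance (set to 1) at baseline and follow-up; correlation ρ between them from 0.2 to 0.8. Once the reference power is fixed, the number of patients cancels.

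**Residual variance of the arm comparison.**
- Raw score, no baseline: 1
- Change score, no baseline: 2(1 − ρ)
- Baseline as covariate, either response: 1 − ρ²

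**Power after adding baseline.** With z = 1.960 + 0.842 = 2.802:
- from a raw score: Φ(z / √(1 − ρ²) − 1.960)
- from a change score: Φ(z × √[2(1 − ρ)/(1 − ρ²)] − 1.960), where the ratio under the root simplifies to 2/(1 + ρ)

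Worked case, ρ = 0.5, raw score: 2.802/√0.75 = 3.235; 3.235 − 1.960 = 1.275; Φ = 0.899. The gain is 9.9 points.

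| ρ | Change-score variance | Adjusted variance | Gain from raw score (points) | Gain from change score (points) |
|---|---|---|---|---|
| 0.2 | 1.60 | 0.96 | 1.6 | 15.1 |
| 0.3 | 1.40 | 0.91 | 3.6 | 13.5 |
| 0.4 | 1.20 | 0.84 | 6.4 | 11.8 |
| 0.5 | 1.00 | 0.75 | 9.9 | 9.9 |
| 0.6 | 0.80 | 0.64 | 13.8 | 7.9 |
| 0.7 | 0.60 | 0.51 | 17.5 | 6.0 |
| 0.8 | 0.40 | 0.36 | 19.7 | 4.0 |

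**Sensitivity to the reference power.** At ρ = 0.5 with a raw score, the gain is 8.1 points from 30%, 11.9 from 50%, 9.9 from 80% and 6.3 from 90%.

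**Sensitivity to repeated visits.** If the contrast averages k visits under compound symmetry, the unadjusted variance is v = (1 + (k − 1)ρ)/k and the adjusted variance is v − ρ². At ρ = 0.5 the values for k = 4 are 0.625 and 0.375, a gain of 15.1 points from 80%. For k = 8 they are 0.5625 and 0.3125, a gain of 16.4 points.

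**Chance imbalance.** If the arms differ by D standard deviations at baseline, the unadjusted contrast is expected to shift by ρD for a raw score and by −(1 − ρ)D for a change score. Baseline adjustment removes this shift.

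**The case against.** The strongest reply is that the SAP does not exclude baseline. It says the model may take other covariates, and the word other can be read as additional to terms already present, given that the QLQ-C30 model just above contains baseline. SAP 5.2.1.3 derives change from baseline for worst pain, so baseline could enter through the response. It could also enter as one of the repeated measures, in which case much of the loss disappears. This stands: a reader might infer that the SAP plans an unadjusted analysis, and the text does not support that. What it shows is a model that need not use baseline.

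Second, the stakes are limited. The main pain measure is time to first worsening of worst pain, which is defined against baseline and tested by a stratified log-rank test. Pain response is also defined against baseline. No power target or confirmatory claim rests on the mixed model. This stands too, and it limits the point to supplementary comparisons.

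Third, the comparison with the other instruments should not be pressed too far. The QLQ-C30 mixed model covers two of fifteen scales, and that instrument's own pain scale has no mixed model. Even so, each PRO mixed model that the SAP describes in any detail names the baseline score.

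The reply does not show that baseline will be used, or that the choice is fixed before results are seen.

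**Conclusion.** The point holds as a gap in specification with a better method available at almost no cost. As written, the mBPI-sf mixed model can be run without the baseline score. It would then be less precise and exposed to chance baseline imbalance, and the choice to adjust remains open.

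The size depends on assumptions. From an assumed 80% reference power at one visit, the gain from adding baseline is about 2 to 20 points for a raw score, and about 15 to 4 points for a change score, as ρ goes from 0.2 to 0.8. A reader might take a loss of about 10 points as the answer. That is only the case ρ = 0.5 with 80% reference power, and neither value is in the documents. A reader might also infer that the pain objective as a whole is weakened. It is not: time to first worsening of worst pain is unaffected, as are OS, PFS and ORR.

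**What to change.** In SAP 5.13 (mBPI-sf), state that the mixed model for each of the four pain items and for the interference mean:

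- has change from baseline as the response;
- includes arm, baseline score of that item (or of the interference mean), cycle, arm-by-cycle and the three IWRS stratification factors of Section 5.3;
- takes its covariance structure by the same rule as the QLQ-C30 model.

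Treat any other covariates as sensitivity analyses. With baseline in the model, raw and change responses give the same arm contrast, so this also settles the response scale.

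The cost is a sentence or two in the SAP, added while the sponsor is still blinded to results by arm. No new data are needed. SAP 5.7.1 already requires a baseline form, so few if any patients should be lost. The possible exceptions are patients whose baseline form lacks the item concerned, since SAP 5.4 counts a form with one item answered as completed for compliance.
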